## 7.5 Additional, Unexpected Follow-Up Visits

If a potential adverse event is reported by the subject or identified during examination, the Investigator or study staff will schedule the subject for an Event Follow-up Visit within 24 hours. At this visit the Investigator or his designee will:

- a. Obtain a complete history of the event in question as well as conduct an examination of the subject and determine if the reported event qualifies as an Adverse Event. If the event is determined to be an Adverse Event, an Adverse Event (AE) case report form and Event Follow-up (EF) Visit case report form must be completed. One AE case report form should be used to track the history of an individual AE throughout the period of the study.
- b. Collect an updated medical and surgical history along with recording of concomitant medications or treatments.
- c. Take photographs of the subject with attention to the area in question.
- d. Render treatment for the event, if any, as determined by the medical judgment of the investigator.

Additional follow-up visits may also be required after the last scheduled visit to assess resolution of adverse events.

## 8. Schedule of Events

Procedures	Pre-Screening	Screening: Visit 1 #	Treatment: Visit 2 (Day 0) #	Follow Up: Visit 3 (Month 3)	Follow Up: Visit 4 (Month 6)
Telephone/Telehealth Screen	X				
Informed Consent		X			
Inclusion/Exclusion Criteria		X			
Demographics		X			

Medical History/Concomitant Medications		X	X	X	X
Physical Exam		X			
Urine Pregnancy		X			
Treatment			X		
Standard Photographs		X		X	X
Surface area assessment using the H2 3D Imaging System and Standup Vectra		X		X	X
Clinician GAIS					X
Non-invasive Skin Tests*		X		X	X
Biopsy			X	X	X
Safety Assessment			X	X	X

# The treatment visit activities may be conducted at the Screening Visit

\* TEWL measurement, OCT images, BTC-2000, and/or high frequency ultrasound images will be taken

#### 9. Statistical Methods of Analysis:

This initial study will include change from baseline analysis.

The primary outcome measure of effectiveness will be a paired comparison of baseline to all applicable post-baseline time points using data obtained from a trans-epidermal water loss assessments, high resolution ultrasonography, optical coherence tomography, BTC 2000 measurements, biopsies results, and 3D imaging results. Photographs and 3D video of treated skin at follow-up visits will be compared to baseline for blinded scoring evaluations. Mean of the change from baseline (defined as post-baseline value minus baseline value) will be estimated at post-baseline time points for applicable parameters.

The following will be calculated and reported for each evaluation parameter at the applicable post-baseline time point(s):

$$\text{Percent mean change from baseline} = \frac{\text{(visit mean score} - \text{baseline mean score})}{\text{baseline mean score}} \times 100$$

For clinician's global aesthetic improvement assessment, the null hypothesis that the mean score is equal to 4 (no change) will be tested.

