## 2. Purpose:

The purpose of this study is to evaluate the safety and efficacy of bipolar fractional radiofrequency treatment via use of the Profound System to achieve skin tightening and contour change in lax submental (beneath the chin) tissue.

Overall assessment of clinical outcome and safety will be based on clinic visits and measurements of volume difference and lift obtained by the Vectra H2 3D Imaging System and Stand-up Vectra (Canfield Scientific, Parsippany, NJ). Additionally, evaluation of pre- and post- procedural photos/video obtained via the 3D Imaging Systems will be performed comparing Baseline and 180 Days by blinded raters. These photos will be identifiable full-face photos, and subjects will be adequately informed of such. Two unblinded clinician's assessments of satisfaction will be characterized using the five-point Global Aesthetic Improvement Scale (GAIS) at the final follow up visit, one based on a live assessment and one based on photos. Subjects will also undergo high-resolution ultrasonography, optical coherence tomography, transepidermal water loss measurements, and/or BTC 2000 measurements for exploratory purposes. Additionally, consenting subjects will undergo two skin biopsies at the treatment site. Micro-biopsies using 0.33mm size punches will be used to extract core tissues before and after treatment for histological evaluation (tissue structure, elastin, collagen and hyaluronic acid expression) and gene expression assessment (elastin, other major extracellular matrix (ECM) molecules and elastin related genes).

From these exploratory procedures the improvement in laxity of the submentum can be evaluated in comparison to pre-treatment assessments.

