## 6.2 Secondary Endpoints

- Improvement in overall lifting of treated tissue in the submental region via Blinded Evaluation of Baseline (pre-procedure) and Day 180 (post-procedure) photos and video obtained via the H2 3D Imaging System and Standup Vectra
- Blinded Reviewers assessment of improvement via the GAIS (Baseline vs. Day 180).
- Subject Assessment of Pain
  - The subjects' assessment of pain will be completed using an 11-point pain scale, where 0 = no pain, 10 = extreme pain (See Appendix A)
- Improvement in skin texture and laxity
  - Micro-biopsies for histology/gene expression
  - High-resolution ultrasound (HRUS)
  - Transepidermal Water Loss Measurements (TEWL)
  - Optical Coherence Tomography (OCT)
  - BTC 2000

Primary Endpoint Analysis:

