#### 10. Blinded Evaluation

Blinded evaluation will be performed by three physicians (dermatologist and/or plastic surgeons) to determine if the Profound System is effective for treatment to lift lax submental (beneath the chin) tissue.

Three qualified, non-treating clinicians will be trained to independently review Baseline and Follow-up photographs for each subject. The reviewers will be blinded to subject information and the temporal order of the photographs. No information will be provided to the reviewers that may allow them to determine the Baseline from the Follow-up imaging.

The pair of scans (labeled A and B) for each subject will include the pre-treatment photographs and post-treatment photographs (6 months follow-up).

The three blinded reviewers will individually be asked to review a randomized presentation of each subject's photographs. Each reviewer will be asked to record if he/she observes a difference between the pair (before and after) of the photographs. If the reviewer determines there is a difference, the reviewer will record which pair (A or B) he/she believes correlates to the Follow-up photographs. Improvement will be based on at least two of the three (2/3) blinded reviewers correctly identifying the post-treatment photographs. Secondarily, each reviewer will score the photo pairs in which they observed a difference for improvement via the GAIS.

Assessments of 2/3 blinded reviewers selecting "no change" will be considered as "no improvement, neither worsening". Assessments of 2/3 blinded reviewers selecting "change" and incorrect identification of the pre and post photographs will be considered as "worsened".

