## 20. Appendix

### A. Numerical Pain Rating Scale

[figure not shown]
[figure not shown]

B. Global Aesthetic Improvement Scale (GAIS)

GAIS	Rating	Description
 1	Very Much Improved	Optimal cosmetic result in this subject
 2	Much Improved	Marked improvement in appearance from the initial condition, but not completely optimal for this subject
 3	Improved	Obvious improvement in appearance from initial condition, but a re-treatment is indicated
 4	No Change	The appearance is essentially the same as the original condition
 5	Worse	The appearance is worse than the original condition

D. Clinician-Reported Submental Fat Rating Scale (CR-SMFRS)

Scale	Description
0	Absent
1	Mild
2	Moderate
3	Severe
4	Extreme

Scale	0	1	2	3	4
Submental Convexity	Absent	Mild	Moderate	Severe	Extreme
Description	No localized submental fat evident	Minimal localized submental fat	Prominent localized submental fat	Marked localized submental fat	Extreme submental convexity
Representative Photographs					
					
					

*Dermatologic Surgery: November 2016 - Volume 42 - Issue - p S263-S270*

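### The plan's only explicitly worded null hypothesis most naturally falls on the unblinded clinician GAIS, which is not a listed endpoint, while the listed blinded evaluation has no study-level test

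*Combined protocol and SAP*

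**What the plan says.** Section 9 (Statistical Methods of Analysis) introduces its one explicit hypothesis with "For clinician's global aesthetic improvement assessment" and continues that "the null hypothesis that the mean score is equal to 4 (no change) will be tested". It names no test statistic, significance level or sidedness.

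Section 2 (Purpose) describes the clinician rating: "Two unblinded clinician's assessments of satisfaction will be characterized using the five-point Global Aesthetic Improvement Scale (GAIS) at the final follow up visit". One rating is made live and one from photographs. The Schedule of Events (Section 8) has a row "Clinician GAIS", marked at Month 6 only, which does not mention blinding.

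Section 6 does not list the clinician rating among the endpoints. The GAIS entry in Section 6.2 is the blinded reviewers' rating, baseline against Day 180.

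Section 10 describes how the blinded data arise. Three non-treating clinicians see each subject's image pair in masked, randomized order and say whether they see a difference and, if so, which image is the follow-up. Agreement of two of three classifies the subject as improved, neither, or worsened. In addition, "each reviewer will score the photo pairs in which they observed a difference for improvement via the GAIS". Neither Section 9 nor Section 10 gives a study-level test, null rate or success threshold for these readings.

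Section 9 also plans a paired comparison with baseline for the instrument, biopsy and 3D imaging measures, without naming a hypothesis or a test.

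**The concern.** The trial is single-arm, uncontrolled and unblinded, with up to 15 subjects (Section 3). For a visual judgement, masking the order of the images is the main protection the design offers, and the plan already provides for it. Yet the one worded hypothesis is attached to ratings made without that protection.

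A clinician who knows the subject was treated may lean towards a favourable grade. An ineffective device then need not produce a mean of 4, and rejecting that value need not mean the device worked. What is at stake is a significant result, reported from the most bias-prone visual outcome, while the masked readings of the same question carry no formal test.

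**Working it through.** The plan gives no power, alpha or effect size for this test, so there is no planned figure to reproduce. The check asks how little rater leaning is enough to reject.

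**Inputs from the documents.** n = 15, the maximum in Section 3. Null mean 4; grade 3 is 'Improved', 4 is 'No Change' and 5 is 'Worse' (Section 20, Appendix B).

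**Assumptions.** One-sample t-test, two-sided 0.05, one rating per subject, no true change. In steps 1 to 3, k subjects are scored 3, the rest 4, and nobody 5.

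**Step 1: t-test.** Mean = 4 − k/15 and t = (mean − 4)/(SD/√15), on 14 degrees of freedom.

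| k scored 3 | Mean | t | p (t-test) | p (exact sign test, 2 × 0.5^k) |
|---|---|---|---|---|
| 3 | 3.80 | −1.87 | 0.082 | 0.25 |
| 4 | 3.73 | −2.26 | 0.041 | 0.125 |
| 5 | 3.67 | −2.65 | 0.019 | 0.0625 |
| 6 | 3.60 | −3.06 | 0.009 | 0.031 |

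For k = 4 the SD is 0.458 and the standard error is 0.458/√15 = 0.118, so t = −0.267/0.118 = −2.26. Four generous scores suffice for the t-test and six for the sign test.

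**Step 2: fewer subjects.** Four also suffice at n = 12 (p = 0.039) and n = 10 (p = 0.037).

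**Step 3: how often this would happen.** Let q be the chance that an unchanged subject is scored 3 rather than 4. The documents give no value, so a range is shown. The rejection probability at n = 15 is P(Binomial(15, q) ≥ 4) for the t-test and ≥ 6 for the sign test.

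| q | t-test | sign test |
|---|---|---|
| 0.1 | 0.06 | 0.002 |
| 0.2 | 0.35 | 0.06 |
| 0.3 | 0.70 | 0.28 |

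**Step 4: leaning or noise?** With symmetric error (20% scored 3, 60% scored 4, 20% scored 5), simulation gives a two-sided error of about 0.05. The inflation comes from leaning, not from imprecise rating.

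**Step 5: sensitivity to one unfavourable score.** If one of the 15 is scored 5, then 4 favourable scores give p = 0.19, 5 give 0.10, 6 give 0.055 and 7 give 0.028. Seven are then needed.

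**Step 6: what null the blinded data supply.** Suppose each reviewer reports a difference with probability d and then guesses. The chance of naming the follow-up image correctly is c = d/2. For independent reviewers, P(at least 2 of 3 correct) = 3c²(1 − c) + c³, which is 0.50 at d = 1, 0.28 at d = 0.7 and 0.16 at d = 0.5. A test of the improved proportion against a fixed rate would therefore depend on an unknown d. The split between improved and worsened does not: with A/B order randomized and masked, swapping the labels exchanges the two outcomes, so each is equally likely under guessing.

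**The case against.** **The paired comparison.** A reader might infer that the GAIS test is the only p-value the plan will produce. The documents do not support that. Section 9's paired comparison of the instrument, biopsy and 3D measures would ordinarily yield p-values, although no test is named. Nor are the blinded readings left without any rule: Section 10 classifies each subject. What stands is narrower: one worded hypothesis, and no study-level test for the blinded evaluation.

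**Who the clinician is.** The sentence in Section 9 does not say unblinded, and Section 10 also calls the blinded reviewers clinicians. The unblinded reading rests on Section 2 and is the more natural one, but it is an inference. If the blinded reviewers were meant, the sentence still needs correcting: they give a GAIS score only where they saw a difference, so a mean of those scores leaves out the no-change readings.

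**Two ratings per subject.** A reader might infer that the live and photo ratings will be pooled as 30 independent values. Nothing says so. The gap is that the plan does not say which rating is tested.

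**Fragility of the figure.** The count of 4 depends on the t-test and on nobody being scored worse, as steps 1 and 5 show. This objection stands in full, and the size of any real leaning is unknown.

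**Exploratory purpose.** Section 1 calls the evaluation exploratory, Section 9 calls this an initial study, and no decision is tied to the test. That limits the consequence. It does not make an unblinded rating the better place for the hypothesis.

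**Conclusion.** The concern holds in limited form. The only explicitly worded null hypothesis most naturally applies to unblinded clinician ratings that Section 6 does not list, while the listed blinded evaluation has no study-level test. A mean of 4 is not a safe null for raters who know that every subject was treated: 4 of 15 one-grade generous scores give p = 0.041.

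That figure assumes a two-sided one-sample t-test at 0.05, one rating per subject and no score of 5. The rejection rates of 0.35 and 0.70 further assume a 20% or 30% chance of generosity. They show what can happen, not what will. It would go too far to infer that the raters will be biased by this amount, or that the lopsided scale by itself causes the problem; unbiased error around 4 leaves the error rate near nominal.

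**What to change.** In Section 9:

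1. Move the formal test to the blinded evaluation, with one value per subject taken from Section 10's existing 2-of-3 classification. Compare improved with worsened subjects by an exact sign test. Count no-change subjects and split readings (no two reviewers agreeing) as ties. State alpha and sidedness.
2. Summarise the blinded GAIS alongside it, counting a reading of no difference as 4.
3. State how a follow-up image that is correctly identified but scored 5 ("The appearance is worse than the original condition") is handled, so that it is not counted as improvement. Section 10 as written would count it so. Without this rule, the classification and the blinded GAIS can contradict each other.
4. Report the live and photo clinician GAIS separately, labelled as unblinded and supportive.

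All these ratings are already planned, so only wording changes. The cost is power. With no subject worsened, six improved subjects are needed (2 × 0.5^6 = 0.031), and ties add nothing. The 50/50 null also relies on the images giving no clue to their order, which Section 10 already requires.

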#### 10. Blinded Evaluation

Blinded evaluation will be performed by three physicians (dermatologist and/or plastic surgeons) to determine if the Profound System is effective for treatment to lift lax submental (beneath the chin) tissue.

Three qualified, non-treating clinicians will be trained to independently review Baseline and Follow-up photographs for each subject. The reviewers will be blinded to subject information and the temporal order of the photographs. No information will be provided to the reviewers that may allow them to determine the Baseline from the Follow-up imaging.

The pair of scans (labeled A and B) for each subject will include the pre-treatment photographs and post-treatment photographs (6 months follow-up).

The three blinded reviewers will individually be asked to review a randomized presentation of each subject's photographs. Each reviewer will be asked to record if he/she observes a difference between the pair (before and after) of the photographs. If the reviewer determines there is a difference, the reviewer will record which pair (A or B) he/she believes correlates to the Follow-up photographs. Improvement will be based on at least two of the three (2/3) blinded reviewers correctly identifying the post-treatment photographs. Secondarily, each reviewer will score the photo pairs in which they observed a difference for improvement via the GAIS.

Assessments of 2/3 blinded reviewers selecting "no change" will be considered as "no improvement, neither worsening". Assessments of 2/3 blinded reviewers selecting "change" and incorrect identification of the pre and post photographs will be considered as "worsened".

The identified reviewers will be instructed that their participation is completely voluntary and has no impact on performance review at their institution. It will be clearly stated that consent is implied with the institution's survey completion. No identifying information about these blinded reviewers will be published but will be maintained in a secure manner to be monitored by the research team. If no incentive is to be provided to the blinded reviewers for their participation, this will be known to them prior to their participation. A waiver of documentation is requested as no subject Personal Health Information (PHI) will be collected, recorded, or shared. Blinded reviewers will be asked to attend one visit for the purposes of evaluating pre procedure photos and post procedure photos via a survey. Prior to the survey, study coordinator will ask for a verbal consent from the reviewers indicating approval to use their responses in the study. Reviewers will assess the images on a local computer.

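### The blinded-lift endpoint counts correct dating of the follow-up photographs as improvement, so a subject graded worse can be recorded as improved; a 1-1-1 vote has no category and no comparison with chance is stated

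*Combined protocol and SAP*

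**What the plan says.** Section 6.2 lists as a secondary endpoint "Improvement in overall lifting of treated tissue in the submental region via Blinded Evaluation of Baseline (pre-procedure) and Day 180 (post-procedure) photos". Improvement by blinded GAIS is listed there as a separate secondary endpoint.

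Section 10 gives the procedure. Three non-treating clinicians, blinded to temporal order, independently view each subject's two image sets (A and B) and say whether they see a difference. If they do, "the reviewer will record which pair (A or B) he/she believes correlates to the Follow-up photographs". The labels follow from those answers:

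- Improved: "Improvement will be based on at least two of the three (2/3) blinded reviewers correctly identifying the post-treatment photographs".
- No improvement, neither worsening: two of three see no change.
- Worsened: two of three see a change, and "incorrect identification of the pre and post photographs will be considered as" worsened.

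GAIS comes afterwards: "Secondarily, each reviewer will score the photo pairs in which they observed a difference for improvement via the GAIS". Grade 5 on that scale (Appendix B) means "The appearance is worse than the original condition".

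Section 9 states one null hypothesis, that the clinician GAIS mean equals 4. For the blinded-lift endpoint the plan gives no test, chance rate, interval or success threshold.

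**The concern.** The endpoint is lift, but the question is about dates. A reviewer can identify the later set because the submentum is tighter, because it looks worse, or because of something unrelated to lift. The rule labels all three cases improved. The protocol itself names visible changes that could reveal the date: pigmentary change and scarring (Section 13), and biopsies taken inside the treated area at treatment and at each follow-up (Sections 7.3 and 7.4). The protocol describes these as rare or small risks. Where they do show, they push the subject towards improved.

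Guessing also produces a share of improved subjects. How large it is depends on how freely reviewers answer no difference, and there is no control arm to show it. Section 10 presents this evaluation as the means of judging whether the device is effective, so a reported percentage improved will be read as evidence of efficacy. It could also contradict the GAIS grades given by the same reviewers in the same session.

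**Working it through.** **No figure to reproduce.** The documents give no power, alpha, chance rate or threshold for this endpoint. The inputs are three reviewers and the two-of-three rules (Section 10), up to 15 subjects with no control (Section 3), and GAIS 5 = worse (Appendix B).

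**Step 1: apply the rule to a worsened subject.** All three reviewers see a difference, all three pick the true follow-up set, and all three grade GAIS 5. Correct datings are 3, which is at least 2, so the label is improved. If each reviewer dates a visibly worse subject correctly with probability c (assumption) and always sees a difference, P(improved) = 3c² − 2c³:

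- c = 0.7: 1.470 − 0.686 = 0.784
- c = 0.9: 2.430 − 1.458 = 0.972

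**Step 2: enumerate the votes.** Each reviewer answers correct, incorrect or no difference, giving 3³ = 27 ordered patterns. Seven are improved, 7 no change, 7 worsened and 6 unclassified. All 6 are the one-correct, one-incorrect, one-no-difference vote. Every 2-1 split is classified.

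**Step 3: chance rates.** Let q be the probability that a reviewer sees no difference (assumption; not in the documents). With no treatment effect and independent reviewers, P(correct) = P(incorrect) = p = (1 − q)/2. Then:

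- P(improved) = P(worsened) = 3p² − 2p³. At q = 0.2, p = 0.4: 0.480 − 0.128 = 0.352.
- P(unclassified) = 6qp². At q = 1/3, p = 1/3: 6/27 = 0.222, the maximum.
- With fully correlated votes (all three react to the same cue), P(improved) = (1 − q)/2.

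The counts for 15 subjects use Binomial(15, P(improved)) with independent reviewers. The last row is the smallest count with upper-tail probability at most 0.025; that level is mine, not the plan's.

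| | q = 0 | 0.2 | 1/3 | 0.5 | 0.8 |
|---|---|---|---|---|---|
| P(improved), independent | 0.500 | 0.352 | 0.259 | 0.156 | 0.028 |
| P(improved), fully correlated | 0.50 | 0.40 | 0.33 | 0.25 | 0.10 |
| P(unclassified), independent | 0 | 0.192 | 0.222 | 0.188 | 0.048 |
| Expected improved of 15 | 7.5 | 5.3 | 3.9 | 2.3 | 0.4 |
| P(8 or more of 15 improved) | 0.500 | 0.117 | 0.022 | 0.0008 | <0.0001 |
| Count needed, of 15 | 12 | 10 | 8 | 6 | 3 |

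The same 8 of 15 is a coin toss at q = 0 and would exceed chance at q = 1/3. No raw count can be interpreted without q.

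**Step 4: a comparison that does not need q.** P(improved) and P(worsened) are equal in every column. Among subjects labelled one or the other, the null split is therefore 50:50 whatever q is, provided nothing in the images reveals the date.

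**The case against.** The strongest reply is that the plan has an implied convention: a reviewer who sees a difference takes the better-looking set as post-treatment. Labelling misdated pairs as worsened makes sense only on that reading. Reviewers are blinded to order, so choosing the worse-looking set as the follow-up may be uncommon. Blinded GAIS is also its own endpoint, so a grade of 5 would be collected and reported. The survey form and the reviewer training are not in the documents and might state the convention.

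Part of this stands: worsening would not be hidden altogether. But the convention is not written down, the written rule can be followed exactly and still give the wrong label, and nothing reconciles the two endpoints. Unseen survey or training material cannot override the protocol text.

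Further points are fair and limit the weight of the concern:

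- The study is exploratory, the endpoint is secondary, and no threshold depends on it. The range for q and the 0.025 level are assumptions.
- The 1-1-1 vote is less frequent if the device works. If reviewers who see a difference are correct 80% of the time (assumption), its share is 6q(1 − q)² × 0.8 × 0.2, which is 12%, 14% and 12% at q = 0.2, 1/3 and 0.5.
- A sign test of improved against worsened does not protect against a cue that reveals the date, because its 50:50 null then fails.

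Reading worsened loosely (two see a change and any one misdates) would absorb the 1-1-1 vote. It would also put a vote of two correct and one incorrect in both improved and worsened, so it does not repair the rule.

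**Conclusion.** The concern holds and should be fixed. The rule is wrong as written, not merely short of detail: it measures whether the follow-up can be recognised, labels that improvement, and can record as improved a subject whom all three reviewers grade as worse. Six of 27 vote patterns have no category, up to 22% of subjects under guessing. The share improved by chance alone runs from 3% to 50% per subject as q goes from 0.8 to 0, assuming independent reviewers and no effect; with fully correlated votes it runs from 10% to 50%. The direction and category faults follow from the text alone and need no assumption. Because no formal decision rests on this endpoint, the consequence is a percentage improved that cannot be read as lift.

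**What to change.** Before the review session, reword the survey question to: which set shows the more lifted, less lax submentum: A, B, or no difference? Then define:

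- Improved: at least two of three choose the true post-treatment set.
- Worsened: at least two of three choose the true baseline set.
- No change: every other pattern, including 1-1-1.

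Report all three counts, an exact 95% confidence interval for the improved proportion out of all evaluated subjects, and an exact sign test of improved against worsened.

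The cost is one reworded question and two or three sentences of analysis, with the same reviewers, photographs and session. The limits should be stated:

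- The sign test drops no-change subjects. At one-sided 0.025 it cannot succeed with 5 or fewer informative subjects (5/5 gives 0.031; 6/6 gives 0.016). With no effect and q = 1/3, about 15 × 2 × 0.259 = 7.8 are informative; 8/8 gives 0.004, 7/8 gives 0.035 and 8/9 gives 0.020.
- If reviewers who see a difference choose the post-treatment set 80% of the time (assumption), power with 15 subjects is about 83%, 70% and 34% at q = 0.2, 1/3 and 0.5. The counts and interval should therefore carry the interpretation, with the test as support.
- Rewording reduces the influence of visible cues but does not remove it: a reviewer who recognises the later set may still favour it.

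### The blinded GAIS omits readings of no difference and does not reorient scores given after a wrong pick, so it can overstate improvement

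*Combined protocol and SAP*

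**What the plan says.** Section 6.2 lists the blinded reviewers' GAIS, baseline against Day 180, as a secondary endpoint. Section 10 describes how it is obtained:

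- Three physicians each view a pair of image sets labelled A and B. "The reviewers will be blinded to subject information and the temporal order of the photographs".
- A reviewer who sees a difference makes a choice: "the reviewer will record which pair (A or B) he/she believes correlates to the Follow-up photographs".
- The GAIS comes second, and not for every pair: "each reviewer will score the photo pairs in which they observed a difference for improvement via the GAIS".
- The closing paragraph of Section 10 covers the two-of-three classification. Two or more readings of no change count as neither better nor worse, and "incorrect identification of the pre and post photographs will be considered as" worsened.

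Appendix B defines a five-grade scale: three improved grades (1 to 3), grade 4 for no change ("The appearance is essentially the same as the original condition"), and one worse grade (5).

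Section 9 adds only this for the blinded reading: "Photographs and 3D video of treated skin at follow-up visits will be compared to baseline for blinded scoring evaluations". For the clinician's GAIS it says that "the null hypothesis that the mean score is equal to 4 (no change) will be tested".

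**The concern.** There are two separate gaps.

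**Readings of no difference have no score.** They correspond to grade 4, but Section 10 collects a GAIS only where a difference was seen. No section enters the missing 4s or sets the denominator. The endpoint as collected describes change given that a change was noticed, which is a different and larger quantity than change in the treated subjects.

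**Scores are not tied to the true order.** The GAIS compares appearance with the original condition, but the reviewer can only guess which image that is. On the ordinary reading, the score treats the image picked as follow-up as the follow-up. If that pick is wrong, a score of improved means that the true baseline looked better. Section 10 gives a rule for wrong picks in the two-of-three classification and none for the individual GAIS scores.

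The study has no control arm, and the other GAIS ratings are unblinded (Section 2). Blinded photograph reading is therefore one of its few protections against expectation bias. Without a rule, a subject can be worsened on one blinded result and improved on the other, and the handling could be chosen after unmasking.

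**Working it through.** The plan states no expected GAIS mean, so there is no figure to reproduce. From the documents: up to 15 subjects and 3 reviewers (15 × 3 = 45 readings at most), grades 1 to 3 improved, 4 no change, 5 worse. Two quantities are assumptions: d, the share of readings in which a difference is seen, and q, the share of those in which the reviewer calls the better-looking image follow-up.

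**1. Omitted 4s.** The mean over all readings is d × (mean of scored pairs) + (1 − d) × 4. Hence

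(mean of scored pairs − 4) = (mean over all readings − 4) / d,

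and the share improved among scored pairs is the share among all readings divided by d.

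| d | 90% | 67% | 50% | 40% |
|---|---|---|---|---|
| Factor 1/d | 1.1 | 1.5 | 2.0 | 2.5 |

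Example with 30% improved (grade 3), 10% worse and 60% no change, so d = 40%:

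- All readings: 0.3 × 3 + 0.1 × 5 + 0.6 × 4 = 3.8, with 30% improved.
- Scored pairs only: (0.3 × 3 + 0.1 × 5) / 0.4 = 3.5, with 0.3 / 0.4 = 75% improved.

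If improved and worse scores balance around 4, omission alone does not move the mean.

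**2. Unoriented scores, no device effect.** Let improved be scored 3. The picked image is scored 3 with probability q and 5 otherwise, so the mean of scored pairs is 3q + 5(1 − q). If the 4s are entered but scores are not oriented, the mean is 4 + d × [3q + 5(1 − q) − 4].

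| q | Scored pairs only | 4s entered, d = 50% | d = 67% | d = 90% | 4s entered and oriented |
|---|---|---|---|---|---|
| 50% | 4.0 | 4.00 | 4.00 | 4.00 | 4.00 |
| 70% | 3.6 | 3.80 | 3.73 | 3.64 | 4.00 |
| 80% | 3.4 | 3.70 | 3.60 | 3.46 | 4.00 |
| 90% | 3.2 | 3.60 | 3.46 | 3.28 | 4.00 |

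Entering the 4s therefore does not remove the lean; orienting by the key does.

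If a quarter of the improved scores are grade 2, the mean improved score is 2.75 and the scored-pair means become 3.88, 3.43, 3.20 and 2.98. The value 3.88 at q = 50% arises because the scale has three improved grades and only one worse grade.

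**3. Both gaps in one illustrative set of 45 readings.** Take 20 readings of no difference, 18 right picks scored 3 and 7 wrong picks scored 3.

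- As collected: 25 scores of 3, mean 3.00.
- 4s entered only: (20 × 4 + 25 × 3) / 45 = 3.44.
- Oriented only: (18 × 3 + 7 × 5) / 25 = 3.56.
- Both: (20 × 4 + 18 × 3 + 7 × 5) / 45 = 3.76.

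**4. Agreement with the two-of-three rule, no device effect.** Subjects with at least two wrong picks are classed worsened. All outcomes for three reviewers were enumerated at d = 50, 67 and 90%, with the better-looking image either independent between reviewers or the same for all three.

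| Among subjects classed worsened | q = 70–90% | q = 50% |
|---|---|---|
| Mean GAIS as collected below 4 | 61–98% | 35–50% |
| Median improved after entering 4s and orienting | 2–31% | 35–50% |

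**The case against.** The strongest reply is that Section 10 says who scores a pair, not how the scores are analysed. Readings of no difference are recorded, and a GAIS among visibly changed pairs shown beside their number would be a legitimate conditional summary. That is true, but the plan does not promise this display, and Section 6.2 lists the endpoint without the condition.

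Second, the link between score and pick is inferred, because the survey form is not in the documents. The order might be revealed before scoring. Nothing in the text supports that, and Section 10 describes the reviewers as blinded to order without exception.

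Third, d and q are assumed. This stands. With q = 50% the wrong-pick bias is about zero, and a wrong pick scored 5 would understate improvement.

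Fourth, the two-of-three result already handles both situations, and primary efficacy comes from 3D imaging. This also stands and limits the severity.

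Fifth, the Section 9 test against 4 might be read as covering the blinded reviewers, who are clinicians too. Section 2 and the GAIS row in the Section 8 schedule point to the unblinded ratings, so no false-positive rate is claimed here.

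Finally, a score of 5 after a wrong pick becomes improved without a grade, and some disagreement with the two-of-three rule remains. Both are fair, and the three-category report is meant to deal with the first.

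**Conclusion.** The concern holds and should be fixed. That readings of no difference go unscored is in the text. Its effect is an identity: departure from 4 and share improved grow by 1/d, from 1.1 times at d = 90% to 2.5 times at d = 40%. The missing orientation rule can create apparent improvement with no device effect (3.6 to 3.2 among scored pairs at a 70 to 90% lean) and creates little or none without a lean. The size depends on assumed d and q and on the ordinary reading that a score follows the reviewer's pick. The two-of-three identification result and the 3D imaging endpoint are not affected.

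**What to change.** In Section 10:

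1. Enter GAIS 4 for every reading of no difference, and keep all subjects and readings in the denominator (up to 45).
2. State that the GAIS treats the reviewer's recorded A/B pick as follow-up. After unmasking, orient each score by the true key in both directions: on a wrong pick, improved becomes worse, worse becomes improved, and 4 stays 4.
3. Report oriented scores as improved, no change or worse over all readings, and list grades 1 to 3 descriptively where they exist. Three improved grades against one worse grade cannot be mirrored grade for grade. A median of the three reviewers per subject with an exact sign test is an acceptable optional summary, not a requirement.

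The cost is a few lines of text and recoding at analysis. No new form field, reviewer, image or visit is needed. The blinded GAIS result may look less favourable, and the main summary has three categories instead of five grades. Some disagreement with the two-of-three result can remain, because that rule equates identification with improvement; the fix reduces it only where there is a lean.
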